5.3.2 Caffeine, alcohol, and tobacco

- During dosing, study participants will abstain from ingesting caffeine- or xanthine-containing products (eg, coffee, tea, cola drinks, and chocolate) for 48 hours before the start of dosing until after collection of the final PK sample.
- During the study, study participants will abstain from alcohol for 24 hours before the start of dosing until after collection of the final PK sample.
- Study participants who use tobacco products will be instructed that use of nicotine-containing products (including nicotine patches) will not be permitted while they are in the clinical unit.

5.4 Screen failures

Screen failures are defined as study participants who consent to participate in the clinical study but are not subsequently entered in the study. A minimal set of screen failure information is required to ensure transparent reporting of screen failure study participants to meet the Consolidated Standards of Reporting Trials publishing requirements and to respond to queries from regulatory authorities. Minimal information includes demography, screen failure details, eligibility criteria, and any SAE.

5.4.1 Rescreening

Individuals who do not meet the criteria for participation in this study (ie, screen failures) may be rescreened. Study participants may be rescreened under conditions such as the following:

- Study participant ingests grapefruit (as beverage, fruit, or supplements) within 72 hours before each administration of study medication.
- If a study participant does not meet the exclusion criteria at Screening or on Day -1 due to an out-of-range laboratory result or a minor illness, he/she can be rescreened once at the discretion of the Investigator.

Study participants may be included if the repeat values for the laboratory screening criteria are within normal ranges and/or if repeat values show normalization of the out-of-range safety

laboratory values, and/or after the study participant makes a complete recovery from the mild illness and if all other screening criteria are met.

Rescreened study participants should be assigned a new study participant number.

Tests that result in ALT, AST, or ALP up to 25% above the exclusion limit may be repeated once for confirmation; if the results are out of range again, the study participant cannot be included.

6 STUDY TREATMENTS

Study treatment is defined as any investigational treatment(s), marketed product(s), placebo, or medical device(s) intended to be administered to a study participant according to the study protocol.

6.1 Treatments administered

A summary of the treatment administered is provided in [Table 6-1](#).

Table 6-1: Treatment administered

Study Treatment Name:	PSL
Dosage formulation:	Tablets
Unit dose strength(s)/Dosage level(s):	25mg and 100mg strength for QD and BID dosing
Route of administration:	Oral
Dosing instructions:	All treatments will be administered orally with 8oz. (240mL) water. The use of beverages between 1h predose and 2h postdose should be limited to a maximum of 100mL (in order to keep groups comparable with respect to period of dosing). Study participants will complete a light meal 30 minutes prior to each morning dose of PSL and will complete a standard meal 30 minutes prior to the evening dose of PSL. Treatments will be administered in an open-label fashion. Study participants will be dosed in an upright position and will remain semi-recumbent until 4h afterwards.
Packaging and labeling:	Padsevonil tablets are manufactured, packaged, and labeled according to Good Manufacturing Practice guidelines and applicable laws or regulations.
Manufacturer:	UCB

BID=twice per day; PSL=padsevonil; QD=once per day

6.2 Preparation, handling, storage, and accountability requirements

The Investigator or designee must confirm appropriate temperature conditions have been maintained during transit for all study treatment received and any discrepancies are reported and resolved before use of the study treatment.

Only study participants enrolled in the study may receive study treatment and only authorized site staff may supply or administer study treatment. All study treatments must be stored in a secure, environmentally controlled, and monitored (manual or automated) area in accordance with the labeled storage conditions with access limited to the Investigator and authorized site staff.

The Investigator, institution, or the head of the medical institution (where applicable) is responsible for study treatment accountability, reconciliation, and record maintenance (ie, receipt, reconciliation, and final disposition records).

In case an out-of-range temperature is noted, it must be immediately reported as per instructions contained in the IMP Handling Manual.

Further guidance and information for the final disposition of unused study treatment are provided in the UP0053 IMP Handling Manual.

6.2.1 Drug accountability

A Drug Accountability form will be used to record study medication dispensing and return information on a by-participant basis and will serve as source documentation during the course of the study. Details of any study medication lost, damaged (due to breakage or wastage), not used, partially used, disposed of at the study site, or returned to the sponsor or designee must also be recorded on the appropriate forms. All supplies and pharmacy documentation must be made available throughout the study for UCB (or designee) to review.

The Investigator (or designee) is responsible for retaining all used, unused, and partially used containers of study medication until returned or destroyed.

The Investigator may assign some of the Investigator's duties for drug accountability at the study site to an appropriate pharmacist/designee.

The Investigator must ensure that the study medication is used only in accordance with the protocol.

Periodically, and/or after completion of the clinical phase of the study, all used (including empty containers)/partially used, unused, damaged, and/or expired study medication must be reconciled and either destroyed at the site according to local laws, regulations, and UCB standard operating procedures or returned to UCB (or designee). Investigational medicinal product intended for the study cannot be used for any other purpose than that described in this protocol.

6.3 Measures to minimize bias: randomization and blinding

Randomization and blinding are not applicable for this open-label study.

Each study participant will receive a 5-digit number assigned at Screening that serves as the study participant identifier throughout the study. The study participant number will be required in all communication between the Investigator or designee.

6.3.1 Procedures for maintaining and breaking the treatment blind

Not applicable.

6.4 Treatment compliance

Study participant compliance will be ensured by the administration of study medication by designated site personnel. Drug accountability must be recorded on the Drug Accountability form.

6.5 Concomitant medication(s)/treatment(s)

6.5.1 Permitted concomitant treatments (medications and therapies)

The following concomitant medications are permitted during the study:

- For elderly study participants with stable conditions, use of chronic medication not interfering with the endpoints of the study and at the discretion of the UCB Medical Monitor will be permitted.
- Paracetamol for the treatment of mild symptoms (eg, headache or other pain), given at most every 6 to 8h, not exceeding 2g/day, and with a total of no more than 5g over 7 days
- Inhaled corticosteroids for seasonal rhinitis
- Oral contraceptives not exceeding 30µg ethinyl estradiol or postmenopausal hormone replacement therapy (HRT) or implants, patches, or intrauterine devices/intrauterine hormone-releasing systems delivering progesterone (for female study participants)

6.5.2 Prohibited concomitant treatments (medications and therapies)

The following concomitant medications are prohibited during the study:

- With the exception of permitted concomitant treatments listed in Section 6.5.1, all prescription or nonprescription medicines are prohibited within 2 weeks or 5 half-lives, whichever is longer, of the respective drug, prior to first administration of PSL and during the study, unless required to treat an AE. This includes all over-the-counter remedies, vitamins, and herbal, and dietary supplements (including St. John's Wort).
- Hepatic enzyme-inducing drugs (eg, glucocorticoids, phenobarbital, isoniazid, phenytoin, rifampicin, etc.) should not be used within 2 months prior to dosing. In case of uncertainty, the UCB Medical Monitor should be consulted.
- Drugs of unknown half-lives are prohibited within 2 weeks before administration of PSL and during the clinical part of the study, unless required to treat an AE.

If a study participant needs or takes any prohibited medication, the Investigator will (where possible) discuss with the UCB Medical Monitor and a decision will be made whether the study participant can continue in the study or must be withdrawn.

6.5.3 Rescue medication

Not applicable.

6.6 Dose modification

No PSL dose modifications are permitted during the study for an individual study participant.

6.7 Treatment after the end of the study

There are no plans for continued study participant care or treatment after the end of the study.

7 DISCONTINUATION OF STUDY MEDICATION AND PARTICIPANT DISCONTINUATION/WITHDRAWAL

7.1 Discontinuation of study medication

Study medication will be stopped if the study participant develops a medical condition (or laboratory abnormality or ECG change) that, in the opinion of the Investigator, compromises the study participant's ability to participate or compromises the study participant's safety.

[figure not shown]
In all cases, the study participant should be followed until the condition has resolved as agreed by the Investigator and the UCB Study Physician. If a study participant discontinues study medication, no restart will be allowed.

7.1.1 Liver chemistry stopping criteria

Discontinuation of study medication for abnormal liver function should be considered by the Investigator when a study participant meets one of the conditions outlined in [Figure 7-1](#) or if the Investigator believes that it is in best interest of the study participant.

Study medication will be discontinued immediately and permanently for a study participant if liver chemistry stopping criteria are met.

Figure 7-1: Liver Chemistry Stopping Algorithm

Abbreviations: ALT=alanine aminotransferase; INR=international normalized ratio; SAE=serious adverse event; ULN=upper limit of normal.

Specific assessments and follow up actions for potential drug-induced liver injury are provided in [Appendix 6](#) (Section [10.6](#)).

7.2 Participant discontinuation/withdrawal from the study

Study participants are free to withdraw from the study at any time, without prejudice to their continued care.

A study participant may withdraw from the study at any time at his/her own request, or may be withdrawn at any time at the discretion of the Investigator for safety, behavioral, compliance, or administrative reasons.

If the study participant withdraws consent for disclosure of future information, the Sponsor may retain and continue to use any data collected before such a withdrawal of consent.

If a study participant withdraws from the study, he/she may request destruction of any samples taken and not tested, and the Investigator must document this in the site study records.

See the Schedule of Activities (Table 1-2) for data to be collected at the time of study discontinuation and follow-up and for any further evaluations that need to be completed.

Study participants should be withdrawn from the study if any of the following events occur:

1. The study participant develops a clinically relevant medical condition (physical or psychiatric) that, in the opinion of the Investigator, jeopardizes or compromises the study participant's ability to participate in the study or makes it unsafe to continue.
2. The study participant is noncompliant with the study procedures or medications in the opinion of the Investigator.
3. The study participant takes prohibited concomitant medications as defined in this protocol.
4. The study participant withdraws his or her consent.
5. There is confirmation of a pregnancy during the study, as evidenced by a positive pregnancy test.
6. The Sponsor or a regulatory agency requests withdrawal of the study participant.
7. The study participant has changes in the ECG that are regarded as clinically significant and/or that worsens over time.
8. The study participant has an ECG that shows an absolute value for QTcB or QTcF ≥ 500 ms or ≥ 60 ms above Baseline.
9. The study participant develops a second- or third-degree atrioventricular block or another clinically relevant change in ECG as determined by the Investigator.
10. The study participant has active suicidal ideation without a specific plan as indicated by a positive response ("Yes") to Question 4 of the "Since Last Visit" version of the C-SSRS. The study participant should be referred immediately to a mental healthcare professional and may be withdrawn from the study based upon the Investigator's judgement of the benefit/risk of continuing the study participant in the study on PSL.
11. The study participant has active suicidal ideation with a specific plan as indicated by a positive response ("Yes") to Question 5 of the "Since Last Visit" version of the C-SSRS. The study participant should be referred immediately to a mental healthcare professional and must be withdrawn from the study.

12. The study participant is suspected of having a serious multiorgan hypersensitivity reaction. Serious suspected multiorgan hypersensitivity cases may be identified and reported to the Sponsor by the Investigator using the following algorithm:

- An AE or laboratory value (as defined below) suggestive of internal organ involvement including but not limited to hepatitis, nephritis, pneumonitis, carditis, colitis, encephalitis, pancreatitis, myositis, arthritis, or hematologic system involvement combined with at least 1 of the following: fever, rash, lymphadenopathy, or eosinophilia.
- Treatment-emergent abnormal laboratory value criteria suggestive of internal organ involvement or eosinophilia:
 - Eosinophils percentage $\geq 10\%$.
 - Eosinophils absolute $\geq 0.5\text{G/L}$.
 - Neutrophils absolute $< 1.5\text{G/L}$.
 - Platelets absolute $\leq 100\text{G/L}$.

Withdrawn study participants should follow a taper schedule if possible unless faster discontinuation is considered necessary in the medical judgement of the Investigator. Investigators should attempt to obtain information on study participants in the case of withdrawal.

Study participants who are withdrawn will be replaced at the discretion of the Investigator and Sponsor.

7.3 Lost to follow up

A study participant will be considered lost to follow-up if he or she repeatedly fails to return for scheduled visits and is unable to be contacted by the study site.

The following actions must be taken if a study participant fails to return to the clinic for a required study visit:

- The site must attempt to contact the study participant and reschedule the missed visit as soon as possible and counsel the study participant on the importance of maintaining the assigned visit schedule and ascertain whether or not the study participant wishes to and/or should continue in the study.
- Before a study participant is deemed lost to follow up, the Investigator or designee must make every effort to regain contact with the study participant (at least 1 phone call and 1 written message to the participant), and document his/her effort (date and summary of the phone call and copy of the written message in the source documents), to complete the final evaluation. All results of these evaluations and observations, together with a narrative description of the reason(s) for removing the study participant, must be recorded in the source documents. The eCRF must document the primary reason for withdrawal.

Should the study participant continue to be unreachable, he/she will be considered to have withdrawn from the study with a primary reason of lost to follow-up documented in the eCRF.

8 STUDY ASSESSMENTS AND PROCEDURES

Study procedures and their timing are summarized in the Schedule of Activities ([Table 1-2](#)).

Protocol waivers or exemptions are not allowed.

Immediate safety concerns should be discussed with the Sponsor immediately upon occurrence or awareness to determine if the study participant should continue or discontinue study treatment.

Adherence to the study design requirements, including those specified in the Schedule of Activities ([Table 1-2](#)), is essential and required for study conduct.

All Screening evaluations must be completed and reviewed to confirm that potential study participants meet all eligibility criteria. The Investigator will maintain a screening log to record details of all study participants screened and to confirm eligibility or record reasons for screening failure, as applicable.

Procedures conducted as part of the study participant's routine clinical management (eg, blood count) and obtained before signing of the ICF may be utilized for screening or baseline purposes provided the procedures met the protocol-specified criteria and were performed within the time frame defined in the Schedule of Activities ([Table 1-2](#)).

The maximum amount of blood collected from each study participant over the duration of the study, including any extra assessments that may be required, will not exceed 500mL. Repeat or unscheduled samples may be taken for safety reasons or for technical issues with the samples.

8.1 Pharmacokinetics

Whole blood and urine samples will be collected for measurement of plasma and urine concentrations of PSL and its metabolites, as specified in the Schedule of Activities ([Table 1-2](#)). Additional samples may be collected at additional time points during the study if warranted and agreed upon between the Investigator and the Sponsor.

Instructions for the collection and handling of biological samples will be provided by the Sponsor. The actual date and time (24 hour clock time) of each sample will be recorded.

Samples collected for analyses of PSL plasma and urine concentration may also be used to evaluate safety aspects related to concerns arising during or after the study.

Genetic analyses will not be performed on these samples unless consent for this was included in the ICF. Study participant confidentiality will be maintained. At visits during which plasma and urine samples for the determination of multiple aspects of PSL will be taken, 1 sample of sufficient volume can be used.

Any changes in the timing or addition of time points for any planned study assessments must be documented and approved by the relevant study team member and archived in the Sponsor and site study files, but will not constitute a protocol amendment. The Institutional Review Board (IRB)/Independent Ethics Committee (IEC) will be informed of any safety issues that require alteration of the safety monitoring scheme or amendment of the ICF.

Instructions and additional details regarding PK and urine sampling are provided in the Laboratory Manual.

The maximum deviations from scheduled sampling times considered irrelevant for PK are defined in [Table 8-1](#).

Table 8-1: Irrelevant time deviations for PK sampling

PK blood sampling times	Deviation from scheduled time considered irrelevant
0 hours (predose)	Within 60 minutes
0.25 to 1.5 hours	2 minutes
2 to 8 hours	5 minutes
12 hours	15 minutes
24 to 48 hours	60 minutes

PK=pharmacokinetic

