1.2 Schema

A schematic of the study design is provided in [Table 1-1](#).

Table 1-1: Study schematic

Cohort A (adults; n=at least 10) and Cohort B (elderly; n=at least 18)																		
Treatment Period																	Follow-up Period	
Period 1A (SD)							Period 1B (MD)										EOS/ EOT Visit	
Day	1	2	3	4	5 to 7	8	9	10	11	12	13 morning	13 evening	14	15	16	17 to 21	22	
	Washout																Washout	
PSL Dose (mg)	200					50 BID	100 BID	200 BID	200 BID	200 BID	200	100	100 BID	100 BID	50 BID			
	Plasma	Plasma	Plasma	Plasma							Plasma							
	Urine	Urine	Urine	Urine							Urine							

BID=twice daily; EOS=End-of-Study; EOT=End-of-Treatment; MD=multiple dose; PK=pharmacokinetic(s); PSL=padsevonil; SD=single dose

Note: BID dosing will be at approximately 8:00am and 8:00pm.

Note: To allow age-dependent effects, elderly study participants will include preferably the following categories: at least 3 males and 3 females from ≥65 to 74 years old and at least 3 males and 3 females ≥75 years old. The elderly study participants will be analyzed as one group. If an effect of age category is observed on PK or safety parameters, the effect of the age category will be explored.

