^a All study participants will complete the “Screening/Baseline” version of the C-SSRS during Screening (assessing the past 6 months) and Baseline (Day -1), followed by the “Since Last Visit” version at subsequent visits.

^b At Screening, Baseline (Day -1) and Day 8, a full physical examination will be performed. On all other days a physical examination is performed, it will be a short physical examination (see Section 8.3.4).

^c Vital signs will be performed before each morning dose of PSL; if feasible; vital sign evaluations will follow the same schedule as ECGs. Blood pressure and pulse measurements should be preceded by at least 5 minutes of rest for the study participant in a quiet setting without distractions (eg, television, cell phones).

^d Serum pregnancy test will be performed for females of childbearing potential at Screening. Urine pregnancy testing will be performed at all other time points indicated.

^e For safety laboratory evaluations that occur on a dosing day, these will be performed before the morning dose/PK sample collection.

^f A 12-lead ECG will be performed after a rest of at least 5 minutes. All ECG recordings will be performed in triplicate at 2 to 3 minute intervals at Screening, Baseline (Day -1), predose and 3 hours after the morning dose on each PSL dosing day and EOS/EOT Visit.

- ^g Study participants will be confined to the study site starting at Baseline (Day -1) and may be discharged on the morning of Day 5 after the assessments are complete, per the discretion of the Investigator. Study participants discharged on Day 5 will be readmitted to the study site on the evening of Day 7. If the Investigator deems it acceptable, study participants may be discharged the morning of Day 17.
- ^h PK plasma samples will be taken at the following time points: (a) Period 1A (single dose): predose on Day 1 and 0.25, 0.5, 0.75, 1, 1.5, 3, 4, 6, 8, 12, 24, 48, and 72 hours postdose (14 samples); (b) Period 1B (multiple doses): predose (morning dose), and 0.25, 0.5, 0.75, 1, 1.5, 3, 4, 6, 8, and 12h after the morning dose (11 samples).
- ⁱ Two blood samples will be collected after multiple doses at steady state (Day 13 predose and 1.5h postdose[$\sim t_{max}$]) for PPB.

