- ^j After the morning urine void and collection of a predose sample (no more than 60 minutes before dosing), PK urine collection will be performed at regular intervals on Days 1, 2, 3, and 4 at the following time points: 0 to <12h; 12 to <24h, 24 to <48h, and 48 to <72h after the single dose (4 samples). On Day 13, PK urine collection will be performed 0 to 12h after the 200mg PSL morning dose (1 sample).
- ^k For study participants prematurely terminating or completing the study, final disposition is recorded at the EOS/EOT Visit. All study participants prematurely terminating from the study should be encouraged to undergo final evaluation procedures, in accordance with the EOS/EOT Visit schedule, as soon as possible after the last dose of study medication.

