4.1.2 Treatment Period

The Treatment Period consists of Period 1A (PSL SD administration) on Days 1 to 7 and Period 1B (PSL MD administration) on Days 8 to 21.

In Period 1A, study participants will receive a single oral dose of 200mg PSL on Day 1, at approximately 8:00am, 30 minutes after a light meal has finished. No study drug will be administered on Days 2 to 7; assessments will be conducted during this time as specified in the Schedule of Activities (Table 1-2). Days 2 to 7 are designated as a 6-day washout.

In Period 1B, study participants will receive multiple oral PSL doses on Days 8 to 15, followed by a 5-day washout (Days 17 to 21). Padsevonil will be administered BID, with one dose in the morning [approximately 8:00am] and one dose in the evening [approximately 8:00pm]. Each morning dose will be administered 30 minutes after a light meal has finished. Each evening dose will be administered 30 minutes after a standard meal has finished. The specific PSL dosing schedule is as follows:

- Day 8: 50mg PSL BID
- Day 9: 100mg PSL BID
- Days 10 to 12: 200mg PSL BID
- Day 13: A morning dose of 200mg PSL and an evening dose of 100mg PSL
- Days 14 and 15: 100mg PSL BID
- Day 16: 50mg PSL BID
- Days 17 to 21: no PSL administration; 5-day washout

Dosing will be stopped in any individual study participant, or across the whole study, if any of the relevant individual or study stopping criteria (detailed in Section 7) are met. Decisions about dosing or study cessation for individual study participants should be discussed first with the UCB Study Physician.

Throughout the study, plasma and urine samples for PK analysis and safety evaluations will be performed according to the Schedule of Activities (Table 1-2). Adverse events and concomitant medications will be recorded throughout the study. Liver function parameters and creatinine clearance will be assessed in each study participant. These parameters are influenced by age; therefore, the acceptance ranges for these tests are wider for the elderly study participants.

Study participants will be admitted to the study site on Day -1 prior to the start of dosing. Per Investigator discretion, study participants may be discharged on the morning of Day 5 through the evening of Day 7. Study participants will be readmitted on the evening of Day 7 and will remain on site until the morning of Day 17, when they may be discharged with the permission of the Investigator.

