2.2.1.3 Other pharmacokinetic variables

The following other PK variables for PSL and the two metabolites of PSL will be assessed during the study (single dose and multiple dose):

For the plasma PK of PSL:

Bound and unbound plasma concentration of PSL in two samples

Single Dose:

- CL/F : apparent total clearance

Multiple Dose

- CL/F_{ss} : apparent total clearance at steady-state

For the plasma PK of the two metabolites of PSL:

Single Dose:

- C_{max} : maximum observed plasma concentration
- AUC_{0-t} : area under the curve from time 0 to the last quantifiable concentration

- AUC: Area under the curve from time 0 to infinity

Multiple Dose

- $C_{\max,ss}$: maximum observed plasma concentration at steady-state
- AUC_{τ} : area under the curve over a dosing interval

For the plasma PK of PSL and the two metabolites of PSL:

- C_{trough} : Measured concentration at the end of a dosing interval at steady state
- t_{\max} : time of C_{\max} or $C_{\max,ss}$
- $t_{1/2}$: Terminal elimination half-life
- $t_{1/2,ss}$: Terminal elimination half-life at steady-state
- AUC_{0-12} : area under the curve from time 0 to 12h after a single PSL dose
- $MR_{AUC_{\tau}}$: Metabolic ratio for AUC_{τ}
- $MR_{C_{\max,ss}}$: Metabolic ratio for $C_{\max,ss}$

For the urine PK

- CL_R : Renal clearance of PSL
- f_e : Fraction of the dose excreted unchanged
- f_{met} : Fraction of the dose excreted as the metabolite

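### The Day 13 12 h plasma sample falls due at the evening dose, but its 15-minute tolerance runs both ways and nothing in the protocol or SAP puts the draw first

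*Protocol*

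**What the plan says.** **Timing of the sample.** Footnote h to the protocol's Schedule of activities (Table 1-2, repeated in SAP Table 2-1) sets the multiple-dose plasma samples at "predose (morning dose), and 0.25, 0.5, 0.75, 1, 1.5, 3, 4, 6, 8, and 12h after the morning dose (11 samples"). Predose is specified for the morning dose only.

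**Timing of the dose.** The note to protocol Table 1-1 says "BID dosing will be at approximately 8:00am and 8:00pm", and section 4.1.2 lists "Day 13: A morning dose of 200mg PSL and an evening dose of 100mg PSL". The two doses are nominally 12 h apart, so the last sample and the evening dose coincide.

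**Tolerance.** Protocol section 8.1 introduces its windows with "The maximum deviations from scheduled sampling times considered irrelevant for PK are defined in" Table 8-1. That table has one row for this time point, "12 hours 15 minutes", under a column for deviations regarded as irrelevant. The same row serves Day 1, which has no evening dose, and Day 13, which has one.

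**Use of the sample.** AUCtau, a primary variable, covers one dosing interval (SAP 2.2.1.1) and is computed by linear up/log down (SAP 9.1). Ctrough is "Measured concentration at the end of a dosing interval at steady state" (SAP 2.2.1.3), with no sample named. t1/2,ss is also planned, and Day 13 has no sample after 12 h.

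**Review.** SAP 9.1 sends samples outside the tolerance window to the data evaluation meeting (DEM). It measures Period 1B time deviations from the last dose on Day 16, although the samples are taken on Day 13.

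**Urine.** Footnote j reads "On Day 13, PK urine collection will be performed 0 to 12h after the 200mg PSL morning dose (1 sample"). It does not say that the collection closes before the evening dose.

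**The concern.** A two-sided tolerance is harmless on Day 1. On Day 13 its later half lies after the next dose. The concentration at the end of the interval may then contain drug from the 100 mg evening dose, yet the only written rule classes the sample as acceptable. Computing the parameters from actual times corrects the clock, not the extra drug.

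The 12 h point closes AUCtau, which also determines CL/Fss. It is the last point available for t1/2,ss, and it may be the source of Ctrough. Contamination raises AUCtau and lengthens t1/2,ss. Protocol section 4.2 gives time-dependent inhibition of apparent clearance, with higher exposure, as the reason for including multiple dosing, and contamination would look like that effect.

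**Working it through.** The plan gives no figure on this point and no half-life, so the size has to be modelled.

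**Inputs from the documents.** 200 mg every 12 h up to the morning of Day 13; 100 mg at 12 h; samples at 0, 0.25, 0.5, 0.75, 1, 1.5, 3, 4, 6, 8 and 12 h; linear up/log down AUC.

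**Assumptions.** One compartment, dose-linear, at steady state, F/V = 1 (it cancels in ratios), half-life 4, 6 or 8 h, ka 1.0, 1.5 or 2.5/h, evening dose at exactly 12 h, sample at 12.25 h, absorption lag 0 or 15 min.

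**Formulas**, with k = ln 2 / half-life and no lag:
- Morning profile: C(t) = 200·ka/(ka−k) × [e^(−kt)/(1−e^(−12k)) − e^(−ka·t)/(1−e^(−12ka))].
- Added by the evening dose after d hours: 100·ka/(ka−k) × [e^(−kd) − e^(−ka·d)].

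**Worked case: half-life 6 h, ka 1.5/h, no lag.** k = 0.1155 and 200·ka/(ka−k) = 216.69.
1. True C(12) = 216.69 × 0.25/0.75 = 72.23.
2. Remaining from earlier doses at 12.25 h: 72.23 × e^(−0.0289) = 70.17.
3. Added by the new dose: 108.34 × (0.9715 − 0.6873) = 30.80.
4. Observed: 70.17 + 30.80 = 100.97, and 100.97/72.23 = 1.398, i.e. +40%.
5. C(8) = 114.66. Log interpolation from 8 h to 12.25 h gives 101.73 at 12 h. The 8 to 12 h area is 4 × (114.66 − 101.73)/ln(114.66/101.73) = 432.3, against a true value of 4 × (114.66 − 72.23)/ln(114.66/72.23) = 367.3.
6. AUCtau moves from 1724.1 to 1789.1, i.e. +3.8%.
7. Log-linear half-life from the 6 h, 8 h and last points moves from 6.0 to 13.1 h.

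**Grid at 15 minutes, no lag:**

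| Half-life (h) | ka (/h) | 12 h concentration | AUCtau | Apparent t1/2,ss (h) |
|---|---|---|---|---|
| 4 | 1.0 / 1.5 / 2.5 | +58% / +90% / +144% | +4.3% / +5.8% / +8.1% | 8.1 / 12.6 / 53.7 |
| 6 | 1.0 / 1.5 / 2.5 | +26% / +40% / +63% | +2.7% / +3.8% / +5.4% | 9.9 / 13.1 / 25.6 |
| 8 | 1.0 / 1.5 / 2.5 | +16% / +24% / +38% | +2.0% / +2.8% / +4.0% | 12.2 / 15.3 / 25.6 |

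At 5 minutes with no lag, the 12 h concentration rises by 6% to 59% and AUCtau by about 1% to 4%.

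**With a 15-minute lag.** No new drug has entered by 12.25 h. The 12 h concentration is 2% to 4% low from decay alone, and AUCtau and t1/2,ss are unchanged.

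**Scale for the primary comparison.** The sample-size section (protocol 9.8, SAP 2.4) assumes a CV of 40%, so SD(log) = √ln(1.16) = 0.385. As a check on that input, its power statement reproduces: 9 per group and ratio 2.0 give noncentrality 0.693/(0.385 × √(2/9)) = 3.82 and power 97.7% (stated 97%). With 10 and 18 participants, SE = 0.385 × √(1/10 + 1/18) = 0.152, and t on 26 df is 1.706. The 90% CI then runs from e^(−0.259) = 0.77 to e^(0.259) = 1.30 times the estimated ratio. If every participant in one cohort were contaminated at the full 15 minutes and none in the other, the AUCtau ratio would shift by a factor of only 1.02 to 1.08.

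**The case against.** Much of the case on the other side stands.

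- **The order may be fixed elsewhere.** Protocol 8.1 places further sampling detail in the Laboratory Manual, and SAP 3.4 leaves accepted time deviations to other documents. What can be said is that the protocol and SAP set no order. Even if the manual does, Table 8-1 would still call a post-dose sample irrelevant, and the SAP would still have no rule for it.
- **Such a sample can be found.** Actual sample times are recorded (protocol 8.1), dose times are listed (SAP 10.1), and the DEM reviews data quality (SAP 3.4). A sample taken after the next dose also sits badly with the definitions of AUCtau and Ctrough. A reader might infer that a contaminated value would inevitably be accepted; the documents support only that it could be. Handling it would be an ad hoc decision.
- **Early absorption is not established.** The 0.25 h sample does not show that drug appears by then; it may equally serve to detect a delay. SAP 4.2.1 allows for a lag time in its plots, and the evening dose follows a standard meal where the morning dose follows a light one. Zero is therefore a genuine lower bound.
- **Ctrough may be safe.** The Day 13 morning predose sample also ends a 200 mg interval and fits the SAP definition equally well. AUCtau and t1/2,ss are not protected in that way.
- **Bias between the cohorts.** A reader might infer it because the elderly are recruited first. That is an order of recruitment. The study runs at one site (SAP 3.7, 4.6) on one schedule, and nothing points to different evening routines. The inference is not supported.

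**Conclusion.** The gap is real and conditional. The sample and the evening dose share a nominal time, the tolerance is two-sided in both periods, and neither document states the order. A post-dose sample could be kept as in-window without referral to the DEM.

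Harm requires a draw after the dose and absorption within minutes. Under the stated model, the effect at 15 minutes runs from none (lag of 15 minutes or more) to +16% to +144% in the 12 h concentration with no lag. In the no-lag case t1/2,ss is prolonged by about half or much more, and AUCtau rises by 2% to 8%. The half-life, ka and lag are assumptions; the documents give none of them.

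The large effects fall on variables classed as other, and on Ctrough only if it comes from this sample. The shift in the primary AUCtau is small beside a 90% CI of about 0.77 to 1.30 times the estimate. Cmax,ss and the single-dose primary variables should not be affected. It would be wrong to read this as a threat to the study's ability to detect the sizable differences it looks for. The change is still worth making because it costs almost nothing. The urine wording is a minor gap.

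**What to change.** 1. **Table 8-1, protocol footnote h and SAP Table 2-1.** Give the Day 13 12 h sample its own entry: due 12 h after the morning dose, drawn within the 15 minutes before that time, and always before the evening dose. The remaining timing error in a concentration drawn 15 minutes early is e^(0.25k), about +2% (half-life 8 h) to +4% (half-life 4 h). AUCtau and t1/2,ss are essentially unaffected, because actual times are used.
2. **SAP 9.1.** Treat any Day 13 12 h sample drawn after the evening dose as a relevant deviation and refer it to the DEM. Exclude that concentration from Ctrough and t1/2,ss. Derive AUCtau by extrapolating to 12 h from the last sample before the evening dose with lambda-z where it can be estimated, and otherwise do not report it. Flag these participants: in the worked case the extrapolated 8 to 12 h portion is 367.3/1724.1, about 21% of AUCtau.
3. **SAP 9.1 and 2.2.1.3.** Measure Day 13 time deviations from the Day 13 morning dose, and name the sample used for Ctrough.
4. **Footnote j, both documents (minor).** State that the predose void applies to Day 13 and that the 0 to 12 h collection closes before the evening dose.

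Cost: one table row, two footnotes in each document and a few sentences in the SAP. No added samples or visits and no change to any dose. The Laboratory Manual should be checked for agreement.
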